#### HIGHLY EFFECTIVE METHODS OF CONTRACEPTION

Male condoms with spermicide

Hormonal methods of contraception including combined oral contraceptive pills, vaginal ring, injectables, implants and intrauterine devices (IUDs) such as Mirena® by WOCBP subject or male subject's WOCBP partner Female partners of male subjects participating in the study may use hormone based contraceptives as one of the acceptable methods of contraception since they will not be receiving study drug

Nonhormonal IUDs, such as ParaGard®

Tubal ligation

Vasectomy

Complete Abstinence\*

\*Complete abstinence is defined as complete avoidance of heterosexual intercourse and is an acceptable form of contraception for all study drugs. Subjects who choose complete abstinence are not required to use a second method of contraception, but female subjects must continue to have pregnancy tests. Acceptable alternate methods of highly effective contraception must be discussed in the event that the subject chooses to forego complete abstinence.

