### 1.4.2 Background on Nivolumab

For a complete review of non-clinical and clinical information, please refer to the BMS-936558 Investigator Brochure (IB).

**a) Non-clinical:** Preclinical animal models of tumors have shown that blockade of Programmed death-1 (PD-1) by monoclonal antibodies (mAbs) can enhance the anti-tumor immune response and result in tumor rejection. Antitumor activity by PD-1 blockade functions in PD-L1+ tumors as well as for tumors that are negative for the expression of PD-L1. This suggests that host mechanisms (ie, expression of PD-L1 in antigen-presenting cells) limit the antitumor response. Consequently, both PD-L1 positive and negative tumors may be targeted using this approach. In humans, constitutive PD-L1 expression is normally limited to macrophage-lineage cells, although expression of PD-L1 can be induced on other hematologic cells as well, including activated T cells. However, aberrant expression of PD-L1 by tumor cells has been reported in a number of human malignancies. PD-L1 expressed by tumor cells has been shown to enhance apoptosis of activated tumor-specific T cells in vitro. Moreover, the expression of PD-L1 may protect the tumor cells from the induction of apoptosis by effector T cells. Retrospective analyses of several human tumor types suggest that tumor overexpression (as measured by IHC) of PD-L1 may permit immune evasion by tumors. PD-L1 expression had been shown to be consistently associated with tumors that are more inflamed and is a major mechanism of immune evasion.

*Reproductive and Developmental Toxicity:* Preliminary new non-clinical safety findings of adverse pregnancy outcomes and infant losses in the absence of overt maternal toxicity have been reported. The findings of increased late stage pregnancy loss and early infant deaths/euthanasia in BMS-936558 (nivolumab) exposed pregnant monkeys suggest a potential risk to human pregnancy if there is continued treatment with BMS-936558 during pregnancy.

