## 4.2 Exclusion Criteria

The presence of any of the following will exclude a patient from study enrollment:

1. Within 6 months prior to study drug administration, clinically significant cardiovascular/cerebrovascular disease defined as follows: cerebral vascular accident/stroke, myocardial infarction, unstable angina, congestive heart failure (New York Heart Association Classification Class  $\geq$  II), bleeding or pulmonary embolism or cardiac arrhythmias that was severe enough to cause hemodynamic compromise.
2. Known human immunodeficiency virus (HIV) or acquired immunodeficiency syndrome (AIDS)-related illness (HIV-positive subjects on combination antiretroviral therapy are ineligible because of the potential for pharmacokinetic interactions with oral THU-Dec. Appropriate studies will be undertaken in subjects receiving combination antiretroviral therapy when indicated.
3. Pregnancy or breastfeeding (pregnant or breastfeeding women are excluded from this study because oral THU-Dec has the potential for teratogenic or abortifacient effects. Because there is an unknown, but potential risk for adverse events in nursing infants secondary to treatment of the mother with oral THU-Dec, breastfeeding should be discontinued if the mother is treated with oral THU-Dec.
4. Other severe acute or chronic medical or psychiatric conditions or laboratory abnormality that may increase the risk associated with study participation or study drug administration, or may interfere with the interpretation of study results, and in the judgment of the investigator would make the patient inappropriate for entry into this study.
5. Has had a prior anti-cancer monoclonal antibody (mAb) within 4 weeks prior to study Day 1 or who has not recovered (i.e.,  $\leq$  Grade 2 or at baseline) from adverse events due to agents administered more than 4 weeks earlier.
6. Has had prior chemotherapy within 2 weeks prior to study Day 1 or who has not recovered (i.e.,  $\leq$  Grade 2 or at baseline) from adverse events due to a previously administered agent and meeting the criteria for organ function described in section 4.1.7 Patients who receive palliative radiation therapy within 1 week prior to day 1 are allowed. Patients on treatment with targeted therapy (like EGFR or ALK TKIs) may start study treatment 5 days from last treatment.  

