# 10.0 STUDY CALENDAR

Trial Period:	Screening Phase		Treatment Cycles a																End of Treatment	Post-Treatment	
Treatment Cycle/Title:	Pre-screening (Visit 1)	Main Study Screening (Visit 2)	1		2		3		4		To be repeated beyond 8 cycles								Discon	Safety Follow-up	Survival Follow Up b
			D1 ±4 days	D15 ±4 days	D1 ±4 days	D15 ±4 days	D1 ±4 days	D15 ±4 days	D1 ±4 days	D15 ±4 days	D1 ±4 days	D15 ±4 days	D1 ±4 days	D15 ±4 days	D1 ±4 days	D15 ±4 days	D1 ±4 days	D15 ±4 days			
Scheduling Window (Days):		-28 to -1																	At time of Discon	30 days post discon	Every 12 weeks post discon
Administrative Procedures																					
Informed Consent	X																				
Inclusion/Exclusion Criteria	X																				
Demographics and Medical History	X																				
Prior and Concomitant Medication Review	X																				
Randomization		X																			
Nivolumab			X	X	X	X	X	X	X	X	X	X	X	X	X	X	X	X	X	X	
THU-Dec			2X/week																		
G-CSF neutropenia prophylaxis			G-CSF (e.g., Neupogen, Granix) Recommended 1X/week if ANC is <1.5 x 10  /L																		
Post-study anticancer therapy status																			X	X	
Survival Status																			X	X	
Clinical Procedures/Assessments																					
Review Adverse Events		X	X	X	X	X	X	X	X	X	X	X	X	X	X	X	X	X			
Full Physical Examination		X																			
Directed Physical Examination		X	X	X	X	X	X	X	X	X	X	X	X	X	X	X	X	X	X		
Vital Signs and Weight	X	X	X	X	X	X	X	X	X	X	X	X	X	X	X	X	X	X			
ECOG Performance Status	X	X	X	X	X	X	X	X	X	X	X	X	X	X	X	X	X	X			
Laboratory Procedures/Assessments: analysis performed by LOCAL laboratory																					
Pregnancy Test – Urine or Serum β-HCG		X																			
CBC with Differential		X	X	X	X	X	X	X	X	X	X	X	X	X	X	X	X	X			
Comprehensive Serum Chemistry Panel		X	X	X	X	X	X	X	X	X	X	X	X	X	X	X	X	X			
Urinalysis		X																			
T3, FT4 and TSH		X	X			X				X				X							
Efficacy Measurements																					
Tumor Imaging		X c				X				X				X							
Tumor Biopsies/Archival Tissue Collection/Correlative Studies Blood																					
Archival or Newly Obtained Tissue Collection		X d			X d																
Correlative Studies Blood Collection		X	X	X	X	X	X	X	X	X	X	X	X	X	X	X	X	X	X		

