- a) Patients will receive Nivolumab every 2 weeks ( $\pm$  4 days per protocol) (4 weeks i.e 2 treatments=1 cycle) until progression (by RECIST v1.1) or unacceptable toxicity. A treatment break for upto 6 weeks for will be allowed upon discussion with study PI
- b) Patients will be monitored post study every 12 weeks ( $\pm$  3 weeks) for post-study treatment status, clinical safety updates and survival; these could be done by review of patient's medical records or contacting patient's medical provider or the subject.
- c) Patients disease will be monitored with CT scans of the chest, abdomen and pelvis after every 2 cycles (i.e prior to every odd cycle  $\pm$  7 days) or sooner if clinically indicated;
- d) Patients who have recent ( $<$ 6 weeks from start of study treatment) tissue biopsy or patients who have had recurrence after surgery within 6 months of surgical resection may be eligible without a fresh biopsy; Rest of the patients will require a biopsy prior to study enrollment. Patients will require a repeat biopsy in 6-10 weeks post treatment prior to cycle 3 of nivolumab. If the biopsy is felt to be high risk by the treating physician or interventional radiologist, an exception may be made upon discussing with the PI.
- e) For Cycle 1 Day 1 (C1D1) labs, screening labs can be used if  $\leq$ 1 week; pregnancy tests need to be done within 24hrs of first dose.

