## 12.2 Secondary End Point

a) *Progression free survival:* It is defined as the time from randomization to the date of the first documented tumor progression (per RECIST v1.1) or death due to anycause. Subjects who die without a reported prior progression will be considered to have progressed on the date of their death. Subjects who did not progress or die will be censored on the date of their last evaluable tumor assessment. Subjects who did not have any on study tumor assessments and did not die will be censored on the date they were randomized. Subjects who started any subsequent anti-cancer therapy without a prior reported progression will be censored at the last evaluable tumor assessment prior to initiation of the subsequent anti-cancer therapy. Progression will be assessed every 6 weeks (from the first on-study radiographic assessment) until disease progression is noted.

b) *Overall survival:* It is defined as the time from randomization to the date of death. A subject who has not died will be censored at last known date alive. OS will be followed continuously while subjects are on the study drug and every 3 months via in-person or phone contact after subjects discontinue the study drug.

c) *Safety and tolerability:* Safety and tolerability objective will be measured by the incidence of adverse events, serious adverse events, deaths, and laboratory abnormalities. Adverse event assessments and laboratory tests are performed at baseline, and continuously throughout the study at the beginning of each subsequent cycle. The safety analysis will be performed in all treated subjects. Descriptive statistics of safety will be presented using

National Cancer Institute (NCI) Common Terminology Criteria for Adverse Events (CTCAE) version 4.0 by treatment arm. All treatment emergent AEs, drug-related AEs, SAEs and drug-related SAEs will be tabulated using worst grade per NCI CTCAE v 4.0 criteria by system organ class and preferred term. On-study lab parameters including hematology, coagulation, chemistry, liver function and renal function will be summarized using worst grade per NCI CTCAE v 4.0 criteria.

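### Section 4.2 requires abstinent female subjects to go on having pregnancy tests, but the Section 10.0 calendar schedules none after the first-dose test

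*Combined protocol and SAP*

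**What the plan says.** The abstinence note under the highly effective methods in Section 4.2 reads: "Subjects who choose complete abstinence are not required to use a second method of contraception, but female subjects must continue to have pregnancy tests". It gives no interval and does not point to the calendar.

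In Section 10.0 the row "Pregnancy Test – Urine or Serum β-HCG" carries one mark, under Main Study Screening. Footnote e adds that "pregnancy tests need to be done within 24hrs of first dose". The row has no mark at any treatment cycle, at discontinuation or in follow-up. In the same block of the table, the row "CBC with Differential" is marked at screening and at every Day 1 and Day 15 visit.

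Section 12.2 c) says that "laboratory tests are performed at baseline, and continuously throughout the study at the beginning of each subsequent cycle". It goes on: "On-study lab parameters including hematology, coagulation, chemistry, liver function and renal function will be summarized".

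On the hazard, Section 1.4.2 reports that the animal findings for nivolumab "suggest a potential risk to human pregnancy if there is continued treatment with BMS-936558 during pregnancy". Exclusion criterion 3 in Section 4.2 says that "oral THU-Dec has the potential for teratogenic or abortifacient effects". Under its Pregnancy heading, Section 8.2.2 requires permanent discontinuation and immediate notification if a subject is found to be pregnant.

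**The concern.** One section imposes a continuing safety duty, and the table that sites work from gives it no time point after dosing starts. A coordinator who follows Section 10.0 exactly would do no on-treatment pregnancy test for an abstinent woman.

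What is at stake is patient safety. Nivolumab is given in both arms and THU-Dec in the combination arm. The duties to stop treatment and to report a pregnancy begin only once it is known. Without a scheduled test, someone following the calendar learns of a pregnancy from symptoms or from the patient's own report, so both steps may come later than they need to. In each 4-week cycle that passes, a woman receives 2 nivolumab doses and, in the combination arm, up to 2 x 4 = 8 days of THU-Dec.

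**Working it through.** The documents state no number of pregnancy tests, so there is no figure to reproduce. The check compares the sections and then makes an illustrative count.

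**Comparison**

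1. Duty: the Section 4.2 note makes continued testing mandatory for female subjects who choose abstinence.
2. Schedule: Section 10.0 gives screening (one mark) and the first dose (footnote e). Tests scheduled after the first dose: 0, in either arm.
3. Possible cover elsewhere: Section 12.2 c) places laboratory tests at the start of each cycle. The parameters it then names are hematology, coagulation, chemistry, liver and renal function; hCG is not among them. The calendar, which is specific to each test, shows hCG at screening only, so the general sentence does not supply the missing time points.
4. Chance of a misread table: the blood count and chemistry rows keep their marks across all Day 1 and Day 15 columns, and the urinalysis row, like the pregnancy row, is marked at screening only. Footnote e also refers only to the first dose. The single mark therefore looks intended.

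**Illustrative count of later cycle starts without a scheduled test**

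Inputs: cycle length 4 weeks (Section 10.0, footnote a); 24 months as the ceiling on treatment (Section 3.4). Assumption, not in the documents: one test at each cycle start.

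Formula: later cycle starts = number of cycles - 1.

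- Four cycles, those numbered individually in the calendar (16 weeks): 4 - 1 = 3.
- 24 months: 24 x 30.4375 = 730.5 days; 730.5 / 28 = 26.09, so 26 full cycles and 26 - 1 = 25.
- Range for 24 months: 24 - 1 = 23 if it is read as 24 cycles; 26 if a 27th cycle starting on day 728 (26 x 28) is counted.

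**Who is reached**

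With 60 patients randomized 2:1 (Section 3.2), 40 receive nivolumab plus THU-Dec and 20 nivolumab alone. The documents do not say how many are women of childbearing potential or how many would choose abstinence, so no trial total can be given.

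**The case against.** The best counter-argument is that the note means only that abstinence waives the second contraceptive method and not the testing. On that reading there are tests for it to refer to: a woman who chooses abstinence at screening is tested then and again around the first dose, and nothing is missing. This reading is possible. It fits the word *continue* poorly, and the sentence that follows in Section 4.2 provides for a subject who later gives up abstinence, so the note appears to look beyond enrolment. If baseline tests are all that was meant, the note still needs rewording.

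A second argument is that Section 12.2 c) already covers the test, since the calendar files it among the laboratory procedures and the list of parameters is a reporting list rather than a list of tests done. It is true that silence in that list does not exclude hCG. But a general sentence does not displace the single mark in the row for this test.

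A third is that Section 4.2 binds sites whether or not the calendar repeats it, so only a frequency is missing. That is fair as far as it goes, but a duty with no time point is easily left undone by staff working from the calendar.

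Two further objections stand. No section sets a per-cycle frequency or a 16-week course, so the counts do not measure a protocol error. And the group that the note reaches may be small, or even empty.

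Readers might also infer more than the documents support. Women using other contraceptive methods are not promised on-treatment tests anywhere, so for them there is no inconsistency. Nor are patients unprotected: the pregnancy exclusion, the contraception rules, pre-dose testing, adverse-event review and examinations remain, and a clinically prompted test is not ruled out.

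**Conclusion.** The point holds as a mismatch between a stated safety duty and the schedule meant to carry it out. After the first dose no pregnancy test is scheduled, during treatment or at discontinuation, although Section 4.2 requires abstinent female subjects to go on being tested and treatment may last up to 24 months.

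This rests on reading the note as reaching beyond baseline, which is the more natural reading but not the only one, and on taking the calendar as the controlling schedule. The counts of 3 and about 25 (23 to 26) illustrate a per-cycle interval; it would be wrong to report them as tests that the protocol requires and omits. The number of women affected is unknown. The primary endpoint, error rates, sample size and analysis are not touched. The change is worth making because the hazard is the protocol's own and the remedy is cheap.

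**What to change.** In the pregnancy-test row of Section 10.0, mark Cycle 1 Day 1, linked to footnote e, and Day 1 of each later 4-week cycle, or another interval that the clinical team states. In Section 4.2, have the abstinence note refer to the times shown in Section 10.0. This is needed at minimum for women who choose abstinence. If only the baseline tests were intended, reword the note to say so.

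Two extensions are recommended as safety improvements: apply the schedule to all women of childbearing potential, because the drug hazard does not depend on the contraceptive method, and add a test at discontinuation. Since Section 4.2 asks these women to use contraception for 23 weeks after the last dose, the clinical team should also say whether any later test is wanted.

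The cost is an edit to one calendar row and one sentence, plus one inexpensive urine or serum hCG test per woman per cycle at Day 1 visits where blood is already drawn. The Cycle 1 Day 1 test already exists under footnote e. With per-cycle testing and a discontinuation test, the addition is 3 + 1 = 4 tests per woman over four cycles and about 25 + 1 = 26 at the 24-month ceiling. Nothing in the statistical plan changes.

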#### LESS EFFECTIVE METHODS OF CONTRACEPTION

Diaphragm with spermicide

Cervical cap with spermicide

Vaginal sponge

Male Condom without spermicide

Progestin only pills by WOCBP subject or male subject's WOCBP partner

Female Condom\*.

\* A male and female condom must not be used together

15. Has received prior therapy with an anti-PD-1, anti-PD-L1, or anti-PD-L2 agent.
16. Has a known history of Human Immunodeficiency Virus (HIV) (HIV 1/2 antibodies).
17. Has known active Hepatitis B (e.g., HBsAg reactive) or Hepatitis C (e.g., HCV RNA [qualitative] is detected).
18. Has received a live vaccine within 30 days of planned start of study therapy.

*Note: Seasonal influenza vaccines for injection are generally inactivated flu vaccines and are allowed; however intranasal influenza vaccines (e.g., Flu-Mist®) are live attenuated vaccines, and are not allowed.*

### 4.3 Inclusion of Women and Minorities

Men, women and members of all races and ethnic groups are eligible for this trial.

## 5.0 REGISTRATION

All subjects who have been consented are to be registered in the OnCore™ Database. For those subjects who are consented, but not enrolled, the reason for exclusion must be recorded. All subjects will be registered through Cleveland Clinic and will be provided a study number by contacting the study coordinator listed on the cover page.

## 6.0 TREATMENT PLAN

Trial treatment should begin on the day of randomization or as close as possible to the date on which treatment is allocated/assigned.

**6.1 Nivolumab:** Nivolumab will be given every two weeks at a dose of 240mg IV to be administered as a 60 minute IV infusion. Subjects may be dosed no less than 12 days from the previous dose of drug. There are no pre-medications recommended for nivolumab on the first cycle. The dosing calculations should be based on the actual body weight at baseline. If the subject's weight on the day of dosing differs by > 10% from the weight used to calculate the original dose, the dose must be recalculated. All doses should be rounded to the nearest milligram. There will be no dose modifications allowed. See section 7 for dose delay guidelines.

#### *Treatment of Nivolumab Related Infusion Reactions:*

Since nivolumab contains only human immunoglobulin protein sequences, it is unlikely to be immunogenic and induce infusion or hypersensitivity reactions. However, if such a reaction were to occur, it might manifest with fever, chills, rigors, headache, rash, pruritus, arthralgias, hypo- or hypertension, bronchospasm, or other symptoms. All Grade 3 or 4 infusion reactions should be reported within 24 hours to the study medical monitor and reported as an SAE if it meets the criteria. Infusion reactions should be graded according to NCI CTCAE (Version 4.0) guidelines.

*Treatment recommendations are provided below and may be modified based on local treatment standards and guidelines, as appropriate:*

**For Grade 1 symptoms: (Mild reaction; infusion interruption not indicated; intervention not indicated):** Remain at bedside and monitor subject until recovery from symptoms. The following prophylactic pre-medications are recommended for future infusions: diphenhydramine 50 mg (or equivalent) and/or paracetamol 325 to 1000 mg (acetaminophen) at least 30 minutes before additional nivolumab administrations.

**For Grade 2 symptoms: (Moderate reaction requires therapy or infusion interruption but responds promptly to symptomatic treatment [eg, antihistamines, non-steroidal anti-inflammatory drugs, narcotics, corticosteroids, iv fluids]; prophylactic medications indicated for 24 hours):** Stop the nivolumab infusion, begin an IV infusion of normal saline, and treat the subject with diphenhydramine 50 mg IV (or equivalent)

and/or paracetamol 325 to 1000 mg (acetaminophen); remain at bedside and monitor subject until resolution of symptoms.

Additional dose modifications (dose delays) of nivolumab are described in Section 7.0

## **6.2 Oral Tetrahydrouridine (THU) and Decitabine (Dec):**

- **THU** is supplied as capsules containing 250 mg of THU per capsule, in bottles containing 8 capsules per bottle. See Section 9 for drug handling and storage recommendations.
- **Dec** is supplied as capsules containing 5 mg of Dec per capsule, in bottles containing 8 capsules per bottle.

**- Starting dose of oral THU and Dec is by weight (all subsequent doses are based on the Cycle 1 Day 1 dose with dose modifications based on toxicities and tumor response as described in the protocol):**

*Weight 40-60kg* = 2 capsules of each drug. Dec capsules are ingested ~60 minutes after THU capsules.

*Weight 61-80kg* = 3 capsules of each drug. Dec capsules are ingested ~60 minutes after THU capsules.

*Weight 81-100kg or higher* = 4 capsules of each drug. Dec capsules are ingested ~60 minutes after THU capsules.

Subsequent dose changes should be based on hematologic parameters, non-hematologic toxicities attributed to study drug or as specified in the protocol.

**- Timing between THU and Dec:** Oral THU capsules followed ~60 minutes later by oral Dec capsules (oral Dec can be taken up to 6 hours after oral THU).

